3.3.2. Benefit Assessment

- All participants will undergo a thorough medical assessment during the study. Participants will have frequent study clinic visits for the evaluation of their disease symptoms. During these visits, participants will have spirometry, ECG, vital signs monitoring, and physical examinations. Monitoring for worsening of their disease will also take place.
- Participants may benefit from the knowledge that they are contributing to the process of developing a new treatment in an area of unmet need, even if not directly beneficial for them
- All participants will continue with changes to their medications, where medically appropriate, to receive established standard of care.

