5. STUDY DESIGN

5.1. Overall Design

A study schematic is shown in [Figure 1](#). This is a parallel group study. Following screening and successful completion of the EXACT daily diary (all participants), rescue medication use daily diary (all participants) and PROactive baseline measurements (questionnaire and participant experience of physical activity) over study days -7 to 1, participants will be randomized (1:1:1:1:1) to receive one of five dose strengths of danirixin (5 mg, 10 mg, 25 mg, 35 mg and 50 mg) or placebo. Study treatment will be administered twice daily for 24 weeks. The PROactive baseline measurements will only be collected for those participants selected for the physical activity monitoring subgroup. Participants who do not properly complete (i.e. are not adherent with the requirements for completing and recording) the required baseline assessments (i.e. EXACT/E-RS:COPD daily diary, physical activity monitoring portion of PROactive, and daily rescue medication use baseline measurements) will not be randomized and will not be eligible for rescreening.

A minimum of three interim analyses are planned for the study. The first interim analysis will be an evaluation of danirixin pharmacokinetics after 10 participants in each treatment group participating in the PK substudy have completed Visit 3.

[figure not shown]
A futility analysis interim based on the E-RS:COPD endpoint and will be conducted after approximately 150 participants have completed 3 months of study treatment.

An additional interim analysis will be conducted approximately 12-15 months after the beginning of the study, or when 450 participants have completed 6 months of treatment, whichever is earlier. This interim analysis will be used to support GSK decisions regarding the further development of danirixin, and will include E-RS:COPD dose response modelling, secondary endpoints of HCRU-defined exacerbations and SGRQ total score along with all available safety data. No changes will be made to the study based on the results of this interim analysis.

Additional informal assessments of danirixin exposure and efficacy data may be undertaken during the conduct of the study as data becomes available. No decisions regarding study conduct will be made based on these informal assessments.

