7.7. Concomitant Therapy

Any medication or vaccine (including over-the-counter or prescription medicines, vitamins, and/or herbal supplements) that the participant is receiving at the time of enrolment or receives during the study must be recorded along with:

- reason for use
- dates of administration including start and end dates
- dosage information including dose and frequency

The Medical Monitor should be contacted if there are any questions regarding concomitant or prior therapy.

The following COPD medications are permitted during the study, at the discretion of the GSK Medical Monitor and/or Investigator:

- Inhaled COPD maintenance medications (e.g. long acting bronchodilator medications (i.e. LAMA, LABA) and long-acting bronchodilator combination

therapies (e.g. LAMA/LABA) and long-acting bronchodilator/inhaled steroid combination (ICS) therapies (e.g. LABA/ICS, LAMA/LABA/ICS)

- Short courses of oral corticosteroids and/or antibiotics (including macrolides) are permitted for the acute treatment of exacerbations of COPD and should not exceed 21 days. This use must be recorded as an HCRU exacerbation event.

The following medications are prohibited from the screening visit until after completion of the follow up visit:

- Chronic use of macrolide antibiotics for the prevention of COPD exacerbations. Examples of chronic use include daily or two-three times per week for at least 3 months.
- Oral or injectable CYP3A4 or BCRP substrates with narrow therapeutic index (CYP3A4 substrates include, but are not limited to, alfentanil, cyclosporine, dihydroergotamine, ergotamine, fentanyl, pimozide, quinidine, sirolimus, tacrolimus, and theophylline; BCRP substrates include, but are not limited to, topotecan.
- Phosphodiesterase-4 inhibitors (e.g. roflumilast)
- Broad spectrum phosphodiesterase inhibitors (e.g. theophylline)
- Chronic use of systemic corticosteroids, i.e. long term (i.e. greater than 3 weeks), daily use of systemic corticosteroids. Chronic use of intranasal, intraocular and topical (for dermatological conditions) corticosteroids is allowed.

GSK will not supply rescue medication. Participants may continue to use and should obtain rescue medication(s) through via their usual route. The following rescue medications may be used:

- Short acting beta agonists (SABA) (e.g., albuterol/salbutamol)
- Short acting muscarinic antagonists (SAMA) (e.g., ipratropium)
- Short acting combination (SABA/SAMA) bronchodilations, (e.g. Duoneb, Combivent)

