10.5.1. Efficacy Analyses

10.5.1.1. Primary Analysis

The primary endpoint is 6 month change from baseline using the mITT population.

Baseline values of E-RS: COPD will be defined as the daily average of scores for the 7 days prior to randomization. Days with missing values will not count towards the average. A minimum of 4 days will be needed and participants without sufficient days will not be randomized.

Individual monthly E-RS:COPD means will be defined as the average E-RS:COPD scores during the following study days:

- Month 1: days 1-28
- Month 2: days 29-56
- Month 3: days 57-84
- Month 4: days 85-112
- Month 5: days 113-140
- Month 6: days 141-168

Days with missing values will not factor into the calculations. Participants will require a minimum number of 10 observations within a month, otherwise the monthly mean will be considered missing for that patient.

The primary analysis will be Emax (4 parameter) modeling of the dose-response curve for the primary efficacy endpoint of month 6 change from baseline. Smoking status will be included as a covariate in this model, allowing the asymptote values of the dose-response relation for smokers to differ from those of the non-smokers. This model formulation will require estimation of at most six parameters. Simpler models nested within this general formulation will be also considered, comprising formulations of the mean dose-response relation allowing for a fixed difference between smokers and non-smokers (parallel curves model), no difference between smokers and non-smokers and the Emax model restriction $m=1$. Model fitness will be measured using standard goodness of fit analysis. This analysis will allow for an assessment of the extent to which the variability of the trial data will be captured using the proposed model and what dose-response specification allows the best interpretation of the data.

The dose-response model will be fitted to the data using Bayesian techniques using the function uniform prior (FUP). The rationale for this choice of inference is that the FUP shrinks the dose-response towards a flat line throughout the dose range, therefore providing more conservative estimates of the dose-response relation compared to maximum likelihood.

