**7.1.1.4. Strategy for Intercurrent (Post-Randomization) Events**

For the primary efficacy analysis, the intercurrent event of interest is occurrence of a protocol deviation considered to impact efficacy during the treatment period (see [Appendix 1](#)). An ‘as treated’ strategy will be used to account for this event - only Month 6 E-RS: COPD data (see Section [14.6.3](#)) collected prior to the occurrence of a protocol deviation considered to impact efficacy will be used in the analysis.

The intercurrent event of treatment discontinuation is accounted for in the endpoint definition as only data at Month 6 will be used.

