## 14. APPENDICES

### 14.1. Appendix 1: Protocol Deviation Management and Definitions for Per Protocol Population

#### 14.1.1. Exclusions from Per Protocol Population

A participant meeting any of the following criteria will be excluded from the Per Protocol population:

Number	Exclusion Description
01	Inclusion #2 – FEV1/FVC ratio $\geq 0.70$ or % predicted FEV1 $< 40\%$ at Screening
02	Inclusion #4 – $< 2$ historical exacerbations or one historical exacerbation with screening fibrinogen $< 3$ g/L
03	Inclusion #5 - Smoking history of $< 10$ pack years at Screening
04	Exclusion #4 - Screening visit is less than 14 days since the completion of a course of antibiotics or oral steroids for a COPD exacerbation
05	Exclusion #14 - Use of PDE4 inhibitors within 30 days of Screening
06	Exclusion #26 - Oxygen use that is not PRN at Screening

At the strategic interim a participant meeting any of the following criteria will be excluded from the Per Protocol population:

Number	Exclusion Description
07	Xanthines at any time between the day after screening and end of treatment
08	PDE4 inhibitors at any time between screening and end of treatment
09	Chronic use (more than 3 months) of erythromycin or azithromycin for between screening and end of treatment
10	Participants who stopped study medication for more than 14 days
11	Blind broken

For the final analysis a participant meeting any of the following criteria will have data excluded from the time of the deviation. If a prohibited medication is taken prior to randomisation the participant will be excluded from the Per Protocol population.

Number	Exclusion Description
07	Xanthines at any time between the day after screening and end of treatment
08	PDE4 inhibitors at any time between screening and end of treatment
09	Chronic use (more than 3 months) of erythromycin or azithromycin between screening and end of treatment
10	Participants who stopped study medication for more than 14 days will be excluded from the PP analyses from the time they stopped taking study medication.
11	Data excluded from date of breaking of blind.

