
 
• For Kaplan-Meier plots of study withdrawal over time, censoring will be performed as follows: 
 
○ Participants are represented from their Day 1 date to the date of early withdrawal from the study (or date of death). Participants that completed the study are censored at the earliest of the date of completion and Day 168.
 
 
 

Medical Conditions and Concomitant Medications
Respiratory Medication Class

 
• COPD concomitant medications will be grouped into the following RMCs based on pre-defined code lists derived from ATC classifications: 
 
○ Androgens and Estrogens
 
○ Anti-IgE, Anti-IL5
 
○ Anticholinergic
 
○ Antiinfectives (antibiotics, antiseptics only)
 
○ Antimycotics
 
○ Antivirals
 
○ Beta 2 Agonist
 
○ Corticosteroid – Inhaled
 
○ Corticosteroid – Depot
 
○ Corticosteroid – Systemic, oral, parenteral and intra-articular
 
○ Corticosteroid – Other
 
○ Leukotriene Receptor Antagonist
 
○ Long-acting anticholinergic
 
○ Long-acting beta-2 agonist
 
○ Mucolytics
 
○ Nedocromil or Cromolyn Sodium
 
○ Oxygen
 
○ PDE4 Inhibitors
 
○ Short-acting anticholinergic
 
○ Short-acting beta-2 agonist
 
○ Xanthine
 
○ Other medication given for exacerbation
 
○ Other COPD medication
 
 
 

COPD Medication Combination

 
• COPD medications will be summarized at the following time points: 
 
○ At Screening: Taken on the day of the Screening visit excluding medications that stopped on the day of the Screening visit
 
○ At Baseline: Taken on the day of start of treatment
 
○ At Month 6: Taken during Month 6 (Study Day 141 to earliest of (Study day 168 and day before study treatment stop date))
 
 
 
• Medication combinations of all RMC categories will be derived. Medications will be summarized based on individual and combinations of the following RMC categories, with or without other medications: 
 
○ ICS
 
○ LABA
 
○ LAMA
 
○ Xanthine
 
○ PDE4 inhibitor
 
○ Anti-IgE, Anti-IL5
 
 
 

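### SAP 14.1.1 does not match protocol 7.7: prohibited chronic systemic corticosteroids have no on-treatment row, and the macrolide row is narrower than the prohibition and gives no exclusion date

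*SAP*

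**What the plan says.** Protocol 7.7 lists medications prohibited from the screening visit until follow-up is complete. One item is "Chronic use of systemic corticosteroids, i.e. long term (i.e. greater than 3 weeks), daily use of systemic corticosteroids". Another is chronic macrolide use to prevent exacerbations, for which the protocol adds: "Examples of chronic use include daily or two-three times per week for at least 3 months". PDE4 inhibitors, broad-spectrum phosphodiesterase inhibitors such as theophylline, and narrow-index CYP3A4 or BCRP substrates are also prohibited.

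SAP 7.1.1 defines the primary estimand in participants who had no deviation considered to impact efficacy and who completed six months. Under SAP 7.1.1.4, only Month 6 E-RS data "collected prior to the occurrence of a protocol deviation considered to impact efficacy will be used in the analysis", and the deviations meant are those in Appendix 1 (14.1.1). SAP 7.1.3.4 uses the same list for the longitudinal model, whose stated aim is the effect had participants kept to the protocol and stayed on treatment.

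For the final analysis, 14.1.1 has five on-treatment rows: xanthines (07), PDE4 inhibitors (08), "Chronic use (more than 3 months) of erythromycin or azithromycin between screening and end of treatment" (09), study medication stopped for more than 14 days (10), and blind broken (11). Data are dropped from the deviation onward. The only steroid item, row 04, concerns a course finished shortly before screening.

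**The concern.** The list removes two kinds of prohibited COPD medication whenever they are used on treatment, but omits a third that can also alter symptoms. A participant on prohibited daily steroids throughout Days 141 to 168 has departed from the protocol. That participant's Month 6 mean nevertheless enters the dose-response as clean data.

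The macrolide row has three smaller mismatches with 7.7: two named agents instead of the class, more than 3 months instead of at least 3 months, and no statement of when exclusion starts. Row 10, by contrast, does state its starting point.

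No other modelled E-RS analysis at the final stage would show the difference. The ITT and Symptomatic populations are confined to the strategic interim (SAP 4.1), and the modelled E-RS tables for the final analysis in SAP 14.11.5 use the per-protocol population. What is at stake is how faithfully the Month 6 curve used for dose selection represents the estimand.

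**Working it through.** **1. The two lists side by side**

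| Medication | Protocol 7.7 | SAP 14.1.1, on-treatment, final analysis |
|---|---|---|
| Xanthines | Prohibited (theophylline) | Row 07, any use after the screening day |
| PDE4 inhibitors | Prohibited | Row 08, any use |
| Systemic corticosteroids, daily, more than 3 weeks | Prohibited | No row |
| Macrolides, chronic, preventive | Prohibited as a class; example is at least 3 months | Row 09: two agents, more than 3 months |
| Narrow-index CYP3A4/BCRP substrates | Prohibited | No row of their own |

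**2. Calendar.** Inputs: "Study treatment will be administered twice daily for 24 weeks" (protocol 5.1) and "Month 6: days 141-168" (protocol 10.5.1.1). Then 24 × 7 = 168 days, and the Month 6 window is 168 − 141 + 1 = 28 days.

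**3. When row 09 can be met.** A course begun on Day s and continued to end of treatment on Day E lasts E − s + 1 days. The row needs E − s + 1 > m, so the last qualifying start day is E − m. The SAP does not convert 3 months to days. I assume m = 91, with a range of 84 (three 28-day study months) to 92. E is 168, or 171 with the Visit 10 window of +3 days.

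| m (days) | E = 168 | E = 171 |
|---|---|---|
| 84 | Day 84 | Day 87 |
| 90 | Day 78 | Day 81 |
| 91 | Day 77 | Day 80 |
| 92 | Day 76 | Day 79 |

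At m = 91 and E = 168, a start on any of Days 78 to 168 (91 of 168 days, 54%) cannot meet the row. A course begun on Days 78 to 141 and continued would still cover the whole Month 6 window.

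**4. What the missing exclusion date does.** If data are cut from first dose, a qualifying participant loses Month 6. If data are cut from the day the threshold is passed (Day s + m), the Month 6 days kept are s + m − 141. A monthly mean needs 10 diary days (SAP 14.6.3), so it survives when s ≥ 151 − m. That is Day 60 at m = 91 (Day 59 at m = 92, Day 67 at m = 84). On this second reading, with m = 91, a course begun on Days 60 to 77 meets the row and still contributes a Month 6 mean recorded on the macrolide.

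**5. The same count for steroids.** With a threshold of more than 21 days, the last start that can pass it by Day 168 is 168 − 21 = Day 147. If data were cut from Day s + 21, the Month 6 days kept would be s + 21 − 141 = s − 120. At least 10 remain when s ≥ 130. A row dated at the threshold would therefore remove the Month 6 mean for continuous courses begun by Day 129 and leave it for later starts.

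**6. Size.** The documents give no rate of such use in any arm. The shift in a dose-placebo difference is the difference between arms in the share affected, times the symptom benefit. As an assumption only, an imbalance of 2 to 10 percentage points and a benefit of 2 to 4 points give 0.02 × 2 = 0.04 to 0.10 × 4 = 0.4 points, in either direction. For scale, with the planning SD of 6.5 and 540/6 = 90 completers per arm, a simple pairwise standard error is 6.5 × √(2/90) = 0.97.

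**The case against.** The strongest reply is that SAP 7.1.1.4 defines an efficacy-impacting deviation by pointing to Appendix 1. The list is thus a chosen subset of prohibited drugs, and the estimand is consistent with it by construction. That is formally right, and narrow-index CYP3A4/BCRP substrates are unlisted too. It does not explain why two prohibited COPD medications are cut and a third is not. It also sits poorly with the longitudinal model's aim of estimating the effect without departures from the protocol.

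On macrolides, the 3-month length comes from the protocol's own example. A course too short for row 09 is therefore mostly not clearly chronic under 7.7 either, and any duration threshold leaves late starts out of reach. This stands. The Day 77 figure describes the row's limits. It does not justify excluding preventive macrolide use of any duration, which would go beyond the protocol. Row 09 could also reach later starts if courses running past end of treatment counted at full length, but its wording does not say so.

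A reader might infer more than the documents support:

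- That all treatment escalation stays in the analysis. It does not: xanthines and PDE4 inhibitors are cut for any on-treatment use.
- That stepped-up inhaled maintenance therapy is a gap of the same kind. Protocol 7.7 permits it, and protocol 3.3.2 expects it: "All participants will continue with changes to their medications, where medically appropriate, to receive established standard of care". It is not a deviation, and a sensitivity analysis for it is optional at most.
- That medication is visible only at Screening, Baseline and Month 6. Beyond those summaries ("At Month 6: Taken during Month 6"), SAP Tables 1.29 and 1.31 show on-treatment COPD medication by class. SAP 7.2.1.5.1 summarises steroid and antibiotic use per moderate or severe exacerbation, and important deviations are tabulated and listed. These displays are descriptive, but they do show use by arm.

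**Conclusion.** The mismatch is real and can be checked from the text. Chronic systemic corticosteroids are prohibited by protocol 7.7 but absent from the on-treatment rows of SAP 14.1.1. Row 09 is narrower than the prohibition and carries no exclusion date. The steroid omission is the firmer of the two. The macrolide point is one of alignment and clarity.

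The Day 77 limit assumes 91 days for 3 months, use counted only to end of treatment, and Day 168 as that end. Other reasonable choices give Day 76 to Day 87.

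The effect on the Month 6 dose-response cannot be derived from the documents and is probably small. A reader might infer that the omission flattens the curve, because rescue by other drugs would be commoner where danirixin works less. That is plausible, but without usage rates by arm neither the size nor the sign is established.

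**What to change.** Reconcile SAP 14.1.1 with protocol 7.7 before the final analysis:

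- Add a final-analysis row for systemic corticosteroid use that meets the protocol's chronic-use definition, with data excluded from the day the use becomes a deviation. Cutting from the first day of the course would also delete acute use that 7.7 permits for exacerbations.
- Reword row 09 to chronic preventive use of any macrolide as the protocol defines it, and state the exclusion date and how months convert to days.
- Report by arm how many participants each row excludes and how many lose their Month 6 mean.

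These are data-handling rules only; nothing changes in what participants may be given. No new data are needed: protocol 7.7 requires dates and reason for use to be recorded, and SAP 14.6.2 already codes systemic corticosteroids and anti-infectives. The cost is SAP wording and reprogramming of the per-protocol exclusions. A few participants would lose Month 6 data. Because the dose-response uses observed Month 6 data only, removing them can itself introduce some selection, and the counts by arm let a reader judge that.

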**14.2. Appendix 2: Schedule of Activities**

**14.2.1. Protocol Defined Schedule of Events**

Procedure	Pre-Screening a (Visit 0)	Screening a (Visit 1)	Study Visits									Early Withdrawal	Follow Up  (up to 28 days post last dose)
			2	3	4	5	6	7	8	9	10		
Study Day			-7	1	14	28	56	84	112	140	168		
Assessment Window	-30 d		± 0d	+ 3d	± 3d	± 3d	± 3d	± 3d	± 3d	± 3d	± 3d		
Eligibility													
Informed consent	X												
Genetic Sample Informed Consent b	X												
Demography	X												
COPD Exacerbation History	X												
Pre-Screening Fibrinogen c	X												
Smoking History d		X											
Smoking Status d		X	X										
Inclusion and Exclusion criteria		X											
Medical history e		X											
Full physical examination including height and weight		X											

**CONFIDENTIAL**

205724

Procedure	Pre-Screening a (Visit 0)	Screening a (Visit 1)	Study Visits									Early Withdrawal	Follow Up  (up to 28 days post last dose)
			2	3	4	5	6	7	8	9	10		
Study Day			-7	1	14	28	56	84	112	140	168		
Assessment Window	-30 d		± 0d	+ 3d	± 3d	± 3d	± 3d	± 3d	± 3d	± 3d	± 3d		
Chest x-ray (CXR) f		X											
HIV, Hepatitis B and C screening g		X											
Pulse Oximetry		X											
Additional Eligibility and In Study Assessments													
Verify Eligibility h			X	X									
Brief Physical				X				X			X	X	X
Urine or serum pregnancy test i		X		X		X	X	X	X	X	X	X	
Laboratory assessments (clinical chemistry (includes liver chemistries), hematology, urinalysis)		X		X		X					X	X	X
Additional Liver chemistries only					X		X	X					
12-lead ECG		X		X		X		X			X	X	
Vital signs	X	X		X		X		X			X	X	
Spirometry		X		X				X			X	X	
Randomization				X									

**CONFIDENTIAL**

205724

Procedure	Pre-Screening a (Visit 0)	Screening a (Visit 1)	Study Visits									Early Withdrawal	Follow Up  (up to 28 days post last dose)
			2	3	4	5	6	7	8	9	10		
Study Day			-7	1	14	28	56	84	112	140	168		
Assessment Window	-30 d		± 0d	+ 3d	± 3d	± 3d	± 3d	± 3d	± 3d	± 3d	± 3d		
Dispense Study Medication				X		X	X	X	X	X			
Dispense log pad and provide training			X										
Dispense MDI sensors and provide training			X										
Dispense physical activity monitor and provide training			X										
Study treatment				←=====→									
Study treatment compliance (ediary)				←=====→									
Collect IP					←=====→					X	X		
Collect MDI sensors												X	X
Collect physical activity monitor												X	X
Collect log pad												X	X
Adverse Event (AE) review				←=====→							X	X	
Serious Adverse Event (SAE) review	←=====→										X	X	

Procedure	Pre-Screening a (Visit 0)	Screening a (Visit 1)	Study Visits									Early Withdrawal	Follow Up (up to 28 days post last dose)
			2	3	4	5	6	7	8	9	10		
Study Day			-7	1	14	28	56	84	112	140	168		
Assessment Window	-30 d		± 0d	+ 3d	± 3d	± 3d	± 3d	± 3d	± 3d	± 3d	± 3d		
Concomitant medication review	X	X	X	X	X	X	X	X	X	X	X	X	X
Clinical Outcomes Assessments													
COPD Exacerbations			←=====→									X	X
EXACT-PRO l			←=====→										
Rescue Medication Use k			←=====→										
SGRQ-C				X				X			X	X	
COPD Assessment Test				X				X			X	X	
PROactive Questionnaire l				X				X			X		
Physical Activity Monitor l			X					X			X		
Participant Global Impression of COPD Severity			X										
Participant Impression of Change in COPD Severity					X	X	X	X	X	X	X	X	

